7.2. Study Rationale

Improvements in TMA markers have been observed in subjects with aHUS and HSCT-TMA. OMS721 has been well tolerated by TMA subjects, by subjects in a Phase 2 study of glomerulonephropathies, and by healthy volunteers in Phase 1 studies. Results from nonclinical toxicity studies of OMS721 and prior clinical experience indicate that there is an adequate safety profile to conduct this study at the proposed doses in subjects with aHUS. A chronic toxicology study supports chronic dosing. Toxicology studies also support dosing in subjects aged 12 and older.

7.2.1. Rationale for Selection of Doses

Pharmacodynamic data in TMA subjects suggest that OMS721 concentrations greater than 5,000 ng/mL may be required to assure high levels of lectin pathway inhibition (>90% inhibition). Pharmacokinetic variability has also been observed. In view of the severe risk in some patients posed by aHUS relapse (e.g., acute renal failure or stroke), targeting a trough plasma concentration greater than 5,000 ng/mL is appropriate to mitigate the risk of aHUS relapse.

Pharmacokinetic modeling and data from healthy volunteers in Study OMS721-NHV-002 indicate that repeating a fixed 150 mg SC dose once daily should provide continuous inhibition

CONFIDENTIAL

No use, disclosure or reproduction outside of Omeros without prior written authorization

of the lectin pathway in most, if not all, subjects. Similar to eculizumab dosing, this dosing regimen is based on achieving trough plasma concentrations that will provide high levels of complement inhibition without breaks. Also, fixed dosing and the use of the adult dosing schedule in adolescents are appropriate based on the weight-, Body Mass Index (BMI)-, and Body Surface Area (BSA)-independent clearance of OMS721. Intravenous loading doses will be used to provide immediate therapeutic plasma concentrations at the initiation of treatment, with plasma therapy, and for rescue if needed.

7.3. Study Endpoints

7.3.1. Primary Endpoint

- Platelet count change from baseline to week 26

7.3.2. Secondary Endpoints

- Safety as assessed by AEs, SAEs, vital signs, ECGs, physical examinations, and laboratory measures
- Complete TMA response defined as normalization of platelet count, normalization of serum LDH, and > 25% decrease in serum creatinine on at least 2 consecutive measures over at least 4-weeks
- Duration of complete TMA response measured from the time of the first measurement of complete TMA response to the last consecutive measurement of complete TMA response
- Time to complete TMA response measured by the time to reach the first measurement of complete TMA response
- TMA event-free status during treatment defined as no decrease in platelet count of > 25% from baseline, no plasma exchange or plasma infusion, and no initiation of new dialysis for at least 12 consecutive weeks
- Time to TMA event-free status measured by the time to reach the first documented TMA event-free status from the first dose of OMS721
- Increase of > 15 ml/min/1.73 m² in eGFR calculated by the MDRD Equation for subjects aged ≥ 18 years and the Schwartz equation for subjects < 18 years
- Time to eGFR increase of > 15 ml/min/1.73 m² measured by the time to reach the first measurement increase in eGFR of > 15 ml/min/1.73 m² from the first dose of OMS721
- Hematological normalization defined as normalization of platelet count and normalization of serum LDH on at least 2 consecutive measurements over at least 4 weeks
- Time to hematological normalization measured by the time to reach the first measurement of hematological normalization from the first dose of OMS721
- TMA remission defined as platelet count ≥ 150,000/µL on at least 2 consecutive measures over at least 2 weeks
- Quality of life as measured by EQ-5D-5L

CONFIDENTIAL

No use, disclosure or reproduction outside of Omeros without prior written authorization

- Serum creatinine change from baseline
- Serum LDH change from baseline
- Serum haptoglobin change from baseline
- Rate of TMA interventions defined as the number of dialysis events, plasma infusion events and plasma exchange events per subject per day over the treatment period
- PK of OMS721
- PD of OMS721
- ADA

7.4. Study Extension

Subjects completing the treatment period may be eligible for extended treatment through either a protocol amendment to extend treatment or expanded access (compassionate use).

8. SELECTION AND WITHDRAWAL OF SUBJECTS

8.1. Subject Inclusion Criteria

Subjects may be included in the study only if they meet all of the following criteria:

1. Competent to provide informed consent or, if a minor, have at least one parent or legal guardian to provide informed consent with written assent from the subject.
2. If an adult, voluntarily provide informed consent in accordance with regulations and governing ethics committee requirements prior to any procedures or evaluations performed specifically for the sole purpose of the study. If a minor, at least one parent or legal guardian must provide informed consent and the subject must provide assent in accordance with local regulations and governing ethics committee requirements prior to any procedures or evaluations performed specifically for the sole purpose of the study.
3. Willing and able to comply with study procedures.
4. Are age ≥ 12 at screening (Visit 1).
5. Have a primary aHUS, diagnosed clinically, and have ADAMTS13 activity $> 5\%$ in plasma. Patients are eligible with or without a documented complement mutation or anti-CFH antibody. Patients are categorized according to their response to plasma therapy (plasma exchange or plasma infusion):
 - a. Plasma therapy-resistant aHUS patients must have all of the following:
 - i. Screening platelet count $< 150,000/\mu\text{L}$ despite at least 4 plasma therapy treatments in a 7-day prior to screening
 - ii. Evidence of microangiopathic hemolysis (at least one of: (1) presence of schistocytes, (2) serum LDH > 1.5 times upper limit of normal (ULN), and (3) haptoglobin $< \text{LLN}$)
 - iii. Serum creatinine $> \text{ULN}$

CONFIDENTIAL

No use, disclosure or reproduction outside of Omeros without prior written authorization

- b. Plasma therapy-responsive aHUS patients must have all of the following:
 - i. Have a documented history of requiring plasma therapy to prevent aHUS exacerbation defined as all of the following:
 1. decrease in platelet count > 25% when plasma therapy frequency has been decreased (including discontinuation of plasma therapy)
 2. LDH > 1.5 times ULN when plasma therapy frequency has been decreased (including discontinuation of plasma therapy)
 - ii. Have received plasma therapy at least once every 2 weeks at an unchanged frequency for at least 8 weeks before first dose of OMS721
6. If sexually active and of childbearing potential, must agree to practice a highly effective method of birth control until the end of the study, defined as one that results in a low failure rate (i.e., less than 1% per year) when used consistently and correctly, such as implants, injectables, combined oral contraceptives, some intrauterine devices, sexual abstinence or vasectomized partner.
7. Do not have access to eculizumab treatment, have not derived therapeutic benefit from eculizumab treatment, or have not been able to tolerate eculizumab treatment.

8.2. Subject Exclusion Criteria

Subjects will be excluded from the study for any of the following reasons:

1. Have STEC-HUS.
2. Have a positive direct Coombs test.
3. Have a history of hematopoietic stem cell transplant.
4. Have HUS from an identified drug.
5. History of vitamin B12 deficiency-related HUS.
6. History of systemic lupus erythematosus.
7. History of antiphospholipid syndrome.
8. Active cancer or history of cancer (except non-melanoma skin cancers) within 5 years of screening.
9. Have been on hemodialysis or peritoneal dialysis for \geq 12 weeks.
10. Have an active systemic bacterial or fungal infection requiring systemic antimicrobial therapy (prophylactic antimicrobial therapy administered as standard of care is allowed).
11. Baseline resting heart rate < 45 beats per minute or > 115 beats per minute.
12. Baseline QTcF > 470 milliseconds.
13. Have malignant hypertension (diastolic blood pressure [BP] > 120 mm Hg with bilateral hemorrhages or “cotton-wool” exudates on funduscopic examination).

CONFIDENTIAL

No use, disclosure or reproduction outside of Omeros without prior written authorization

14. Have a poor prognosis with a life expectancy of less than 3 months in the opinion of the Investigator.
15. Are pregnant or lactating.
16. Have received treatment with an investigational drug or device within four weeks of the screening visit.
17. Have abnormal liver function tests defined as ALT or AST > 5 times ULN.
18. Have HIV infection.
19. History of cirrhosis of the liver.
20. Are an employee of Omeros, an Investigator, a study staff member, or their immediate family member.
21. Have a known hypersensitivity to any constituent of the product.
22. Presence of any condition that the Investigator believes would put the subject at risk or confound the interpretation of the data.
23. Have previously completed treatment in an OMS721 study.
24. Have received intravenous immunoglobulin (IVIG) treatment within 8 weeks of screening visit.
25. Have received rituximab within 24 weeks of screening visit.

8.3. Subject Withdrawal Criteria

8.3.1. Early Discontinuation of Study Drug Administration

Subjects may voluntarily withdraw from the study at any time for any reason without prejudice to further treatment. A subject must permanently discontinue study drug under any of the following circumstances:

- Diagnostic evaluations demonstrate subject does not have primary aHUS.
- The subject becomes pregnant. Study drug must be discontinued immediately and the pregnancy reported to the Sponsor.
- The subject or subject's legal guardian wishes to discontinue study drug treatment for any reason.
- The subject experiences a medical emergency that necessitates discontinuing study drug treatment.
- The subject receives a prohibited concomitant therapy.
- The Investigator, Sponsor, or subject's primary care physician decides to discontinue treatment for medical reasons or due to the subject's noncompliance with the protocol.

The reason for termination of study drug before study completion must be recorded in the subject's case report form (CRF). The subject should complete all scheduled study Follow-Up visits provided that written consent to do so has not been withdrawn. Subjects who discontinue study drug prematurely will not be replaced.

CONFIDENTIAL

No use, disclosure or reproduction outside of Omeros without prior written authorization

8.3.2. Subject Withdrawal from the Study

A subject must be withdrawn from the study and discontinue study drug under the following circumstances:

- The subject or subject's legal guardian wishes to withdraw consent to participate in the study.
- The Investigator or subject's primary care physician decides that the subject should be withdrawn from the study.
- The Sponsor decides that the subject should be withdrawn or the Sponsor discontinues the study for any reason.

The reason for withdrawal must be recorded in the subject's CRF. The subject should complete the evaluations scheduled for the last Follow-up visit, provided written consent to do so has not been withdrawn. Subjects who are withdrawn may be replaced at the discretion of the Sponsor in consultation with the Investigator in order to meet study objectives.

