9.1.2. Blinding

No blinding is necessary in this study.

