10.2.2. Prohibited Concomitant Therapies

Administration of eculizumab is prohibited during the study. If the Investigator decides to administer eculizumab, the subject should be withdrawn from the study.

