13.2.4.1. Handling of Missing Data

Unless otherwise specified, statistical analyses will be based on observed data without imputation.

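### Protocol sections 8.3.1 and 8.3.2 give conflicting replacement rules for treated subjects who are withdrawn, and 8.3.2 leaves replacement to the Sponsor with no criterion independent of response

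*Protocol*

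**What the plan says.** Protocol section 8.3.1, on early discontinuation of study drug, states: "Subjects who discontinue study drug prematurely will not be replaced". Section 8.3.2, on withdrawal from the study, states: "Subjects who are withdrawn may be replaced at the discretion of the Sponsor in consultation with the Investigator in order to meet study objectives".

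Section 8.3.2 opens its list of reasons with "A subject must be withdrawn from the study and discontinue study drug under the following circumstances", so withdrawal from the study entails stopping drug. One of the reasons is "The Sponsor decides that the subject should be withdrawn or the Sponsor discontinues the study for any reason".

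Other provisions that bear on this:

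- **Blinding (9.1.2):** "No blinding is necessary in this study".
- **Interim analysis (13.2.14):** the primary efficacy analyses are run when about 40 FAS patients have at least 26 weeks of follow-up. Both the DMC and the Sponsor review the results.
- **Missing data (13.2.4.1):** "Unless otherwise specified, statistical analyses will be based on observed data without imputation".
- **FAS (13.2.4.2):** all treated subjects with at least one post-baseline platelet count.
- **Sample size (13.1):** 56 plasma therapy-resistant subjects and 80 in total, with the 80 counted as subjects who meet the FAS criteria.

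**The concern.** The two replacement rules do not cover separate groups. A treated subject withdrawn before completing treatment has also stopped drug prematurely. That subject is not replaceable under 8.3.1 and replaceable under 8.3.2.

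Use of eculizumab shows this with a single event. In 8.3.1 a reason for stopping drug is "The subject receives a prohibited concomitant therapy", which leads to no replacement. Section 10.2.2, which names eculizumab as prohibited, says "If the Investigator decides to administer eculizumab, the subject should be withdrawn from the study", which leads to possible replacement. Those sections must be reconciled. This review takes no view on which status is right.

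The permissive rule is also open-ended. Its only criterion is meeting study objectives, and the primary objective is the platelet change itself. No list of reasons, cap or deadline is given, and nothing separates the decision from the platelet results. If replacements are added when the estimate falls short and omitted when it does not, the final number of subjects depends on the results. The ordinary 95% interval makes no allowance for that.

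**Working it through.** **Inputs (protocol 13.1).** True mean change 78, null mean 45, SD 64 (all × 10⁹/L), two-sided 5% t-test, 56 resistant subjects, stated power 90%, resistant share 70%. No withdrawal rate is stated.

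**1. The plan's own figure.** For a one-sample t-test the noncentrality is (78 − 45)/64 × √n.

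- At n = 56 it is 0.5156 × 7.483 = 3.86. Power is 96.6% (noncentral t), or 97.1% by normal approximation, Φ(3.86 − 1.96). The stated 90% is not reproduced.
- 90% power needs n = 42 (t), or 40 by normal approximation: (64 × (1.960 + 1.282)/33)² = 39.5.
- An allowance of 25% for losses would give 42/(1 − 0.25) = 56, but the protocol states none.
- The total does follow: 56/0.70 = 80.

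The gap is conservative. Here it matters only as reserve power.

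| Resistant subjects analysed | Power |
|---|---|
| 56 | 96.6% |
| 45 | 92.3% |
| 42 | 90.4% |
| 39 | 88.1% |

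Up to 56 − 42 = 14 subjects (25%) could be lost with 90% power still met.

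**2. What replacement can do to the number analysed.** A withdrawn subject with one post-baseline count stays in the FAS. Replacement therefore adds subjects, at most as many as were withdrawn, and the FAS could exceed 80. It cannot remove anyone.

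**3. Error when replacement depends on the result.** Simulate under the null (mean 45, SD 64; 400,000 trials). Compute T = (x̄ − 45)/(s/√n) and declare success if T exceeds the 97.5th percentile of t with n − 1 degrees of freedom. Test at n = 56. Only if that fails, add k replacements and test once more at 56 + k. The values of k are assumptions.

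| Replacements k | Share of 56 | One-sided error |
|---|---|---|
| 0 | 0% | 2.5% |
| 3 | 5% | 3.0% |
| 6 | 11% | 3.2% |
| 11 | 20% | 3.4% |
| 17 | 30% | 3.6% |

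**4. Sensitivity to retention.** Step 3 gives each withdrawn subject a full value. At the other extreme, suppose 11 withdrawn subjects contribute nothing at week 26. Testing at 45 and, only if that fails, at 56 gives about 3.5%, so the conclusion does not depend on this choice.

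**5. Error when replacement is automatic.** If withdrawals are unrelated to outcome, lost from the week-26 mean and always replaced, the error stays at 2.5% for 3, 6 or 11 replacements (200,000 trials each). The inflation comes from the discretion, not from replacement as such.

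**The case against.** The strongest defence is that FAS retention leaves the Sponsor little room, and this largely stands. A reader might infer that the Sponsor can choose the number analysed. The documents do not support that: there is no separate evaluable set, and replacement is bounded by the number withdrawn.

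A reader might also infer that the Sponsor sees every platelet count. The open-label design makes that plausible, but what the documents state is Sponsor review of one interim analysis.

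Larger error rates can be produced. A look after each of 11 replacements gives 4.6% if withdrawn subjects are discarded and 4.3% if they are kept. Waiting for week 26 after each one would take 11 × 26 = 286 weeks, about 66 months, against a planned study of about 60. Overlapping enrolment would shorten this, but subjects already dosed with a count cannot be taken back out. One further look is the reasonable case.

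The most tempting reading is that poor responders could be withdrawn and replaced. If the 3, 6 or 11 lowest responders were withdrawn, lost from the mean and replaced, the mean would shift by 6.7, 11.5 or 17.4 × 10⁹/L and the error would be 15%, 35% or 65%. That is an outer bound. It requires perfect selection on outcome and loss of all their data, whereas the repeated-measures model in 13.2.8.1 uses visits before withdrawal. Nothing in the documents indicates such selection.

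It can also be said that 13.2.1 calls all summaries descriptive and that no analysis section sets a success criterion against 45. That is fair. However, 13.1 frames a test against 45, and a 95% lower limit above 45 is the same event as one-sided significance at 2.5%.

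**Conclusion.** The contradiction between 8.3.1 and 8.3.2 is established by the text and needs no assumption. So is the absence of any response-independent criterion for replacement.

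The statistical consequence is modest: a one-sided error of about 3.0–3.6% instead of 2.5%. It rests on 3 to 17 assumed replacements in a cohort of 56, used only while the result is not above 45, with one further look. It also treats the one-sample t-test in 13.1 as the decision rule, which approximates the planned repeated-measures analysis. With automatic replacement and withdrawal unrelated to response there is no inflation.

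No result of this trial is affected. The SAP reports that the study was discontinued (section 2), that the primary objective will not be analysed (4.1) and that there will be no efficacy analysis (9.1). The correction applies to the protocol as written and to any reuse of its text.

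**What to change.** Put one rule in both 8.3.1 and 8.3.2:

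> Subjects in the FAS are not replaced, whether they discontinue study drug or are withdrawn from the study; they remain in the FAS and count toward the planned 80. Only subjects who do not meet the FAS criteria (not dosed, or no post-baseline platelet count) are replaced, and this is done automatically, without reference to platelet results.

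This agrees with the target in 13.1, which counts subjects meeting the FAS criteria, and with the definition in 13.2.4.2.

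The cost is a short amendment and fewer week-26 observations if many subjects withdraw. The reserve in the sample size covers the loss of up to 14 of 56 resistant subjects at 90% power.

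One consequence should be accepted knowingly. Section 7.1 lets resistant subjects be dosed before the Shiga toxin, HIV and ADAMTS13 results and discontinues them if an assay is positive. Those with a post-baseline count would stay in the FAS and count toward the 80. If the Sponsor wants them replaced, that should be a named exception fixed in advance, since its reason does not depend on platelet response.

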8.3.3. Notification of Withdrawal

When a study participant, voluntarily or involuntarily, is discontinued from the study protocol, the Sponsor and the ethics committee will be notified and provided with the reasons for subject discontinuation from this study protocol.

9. STUDY DRUG AND TREATMENT OF SUBJECTS

[figure not shown]
OMS721 is manufactured under current Good Manufacturing Practices (cGMP) for investigational use. OMS721 is a human IgG4 mAb directed against MASP-2.

9.1. OMS721 Drug Product

9.1.1. Packaging and Labeling of Drug Product

CONFIDENTIAL

No use, disclosure or reproduction outside of Omeros without prior written authorization

The vials and single outer cartons will be labeled in accordance with applicable regulations, including at a minimum the following information:

- Name of the drug product [REDACTED]
- Product identification number
- Regulatory cautionary statement regarding investigational or clinical trial use

9.1.2. Blinding

No blinding is necessary in this study.

9.1.3. Dose Preparation

Prior to preparation, the study drug should be inspected for any particulate matter or discoloration. If any particulate matter or discoloration is observed, the vial should not be used.

A high-contrast, black and white image showing a dark, irregular shape on the left and a bright, white shape on the right, separated by a thin black line.

9.1.3.1. Supplemental Drug Administration for Subjects Receiving Plasma Therapy

Treatment Induction Period

If the subject receives plasma therapy on Day 1 or Day 4 of the Treatment Induction Period, the regularly scheduled OMS721 dose will be administered within one (1) hour after completion of plasma exchange or within one (1) hour before plasma infusion. [REDACTED]

Treatment Maintenance Period

If plasma exchange is performed at any time during the Treatment Maintenance Period,

11. **What is the primary purpose of the study?** (check all that apply)

CONFIDENTIAL

No use, disclosure or reproduction outside of Qmeros without prior written authorization

If plasma infusion is performed at any time during the Treatment Maintenance Period, [REDACTED]

[REDACTED]

The total number of IV supplemental doses cannot exceed 4 supplemental doses per week.

Rescue Therapy

If the subject receives plasma therapy on Rescue Therapy Day 1, the regularly scheduled OMS721 IV dose will be administered within one (1) hour after completion of plasma exchange or within one (1) hour before plasma infusion.

[REDACTED]

9.1.4. Storage and Handling of Drug Product

OMS721 Drug Product vials are to be stored according to the Investigator's Brochure.

[REDACTED]

[REDACTED]

[REDACTED]

[REDACTED]

[REDACTED]

[REDACTED]

9.2. Study Drug Accountability

In compliance with U.S. Food and Drug Administration (FDA), European Medicines Agency (EMA), and other applicable regulations, records will be maintained by the Investigator and/or pharmacist designee for OMS721 study drug product delivery to the site, the inventory at the site, the use of each vial, and the return of used and unused drug product, including dates and quantities. The Investigator and/or pharmacist designee will maintain the investigative site's study drug accountability documentation. After the study has been completed, a copy of the Investigator/pharmacy drug accountability records will be provided to the Sponsor. The original drug accountability records will be retained by the site.

The Investigator (or designee) and/or Pharmacist designee is responsible for reconciling and documenting (in the study drug accountability logs) the number of vials dispensed to the subject, the number of vials used by the subject and the number of used and unused vials returned by the subject during the days study drug is self-administered at home. Any study drug issues must be

CONFIDENTIAL

No use, disclosure or reproduction outside of Omeros without prior written authorization

resolved and documented appropriately. Any used or unused study drug can only be destroyed or returned to Omeros after being reviewed by the responsible Omeros Study Monitor. However, if the institution's policy does not allow any used study drug to be stored, the site may destroy any returned/used study drug on site in accordance with the institution's applicable SOP, local laws and regulations. Omeros may request a copy of or request to review the SOP.

